4.3. Exploratory Endpoint

- Elasticity measurement at Days 90 and 180.

Investigational Device: ThermiRF

Protocol No.: Thermi_0005

Version Date: Final 10-May-2016

5. OUTCOMES MEASURE

5.1. Primary Outcomes measure

Overall tissue lift at the submental area as determined by quantitative assessment at Day 90 compared to baseline based on 3D photography.

5.2. Secondary Outcomes Measure

Overall improvement in submental area as determined by qualitative assessment at Day 90 compared to baseline based on 2D photography and subjective questionnaire.

Investigational Device: ThermiRF

Protocol No.: Thermi_0005

Version Date: Final 10-May-2016

6. INVESTIGATIONAL PLAN

6.1. Overall Study Design and Plan

This is an open-label, single-center, single-treatment prospective evaluation of the ThermiRF device in the treatment of submental skin laxity. The purpose of this prospective study is to determine the effectiveness and safety of the ThermiRF device in achieving overall submental lift.

In this study, “Lift” is defined as a ≥ 20 mm² lift of the submental area after the ThermiRF treatment.

A total of 70 male and female healthy volunteers between the age of 35 and 65 will be considered for this study. Subjects who sign the informed consent form and meet all entry criteria will be enrolled in this study and will be assigned a unique number/code to preserve confidentiality.

A total of six study visits are planned as described below:

- Visit 1: Screening visit – (Day 1)
- Visit 2: Single Treatment visit
- Visit 3: Day 30 safety assessment (± 7 to 14 days)
- Visit 4: Day 60 safety and Image capture for validation exercise (± 7 to 14 days)
- Visit 5: Day 90 safety and effectiveness follow-up visit (± 7 to 14 days)
- Visit 6: Day 180 safety and effectiveness follow-up visit - (± 7 to 14 days)

Photo images (2D and 3D) will be collected at Visits 1, Visit 4 (on first 30 subjects only), and at Visits 5 and 6 using a standard camera (2D) and the Vectra XT system (3D). The purpose of the photos are to quantitatively and qualitative evaluate treatment effectiveness using objective and subjective assessments to measure physical changes to the skin’s microstructure and aesthetic skin features over time.

A skin elasticity assessment using the Cutomer® will be collected at Visits 1 (screening), 5 (Day 90) and 6 (Day 180) to assess if any biomechanical changes of the skin occurred as a result of the ThermiRF treatment.

Safety assessments will be collected using the Numerical Rating Scale (NRS) a 10-point scale, and adverse events reports (observed or reported).

The overall study duration is approximately 12 months (i.e., 5-6 month recruitment period and 6 month study visits).

6.2. Discussion of the Study Design and Subject Selection

The study design represents a prospective evaluation of the ThermiRF system effectiveness in the treatment of submental laxity through electrocoagulation and neocollagenesis towards achieving Lift. Submental laxity is a common occurrence of the aging population affecting not only the submental area near the upper part of the neck but also the jawline. For the purposes of this study, subjects between the ages of 35 and 65 years old, are likely to show architectural changes of aging on the submental area, with a clearly noticeable

Investigational Device: ThermiRF

Protocol No.: Thermi_0005

Version Date: Final 10-May-2016

“mild to moderate” severity defined as having “*normal*” muscle, “*mild to moderate*” skin laxity and “*mild to moderate*” fat. Subject’s skin laxity severity will be confirmed by the investigator at the screening visit to ensure appropriateness in subject selection. In an effort to eliminate variance across the group and with respect to treatment response, each subject will serve as his/her own control

The application of RF treatment on this category of subjects is “superficial” in nature with no adjuvant therapies needed. It is anticipated the benefits will be “lift” of the treated (submental) area following a minimally invasive approach resulting in less adverse outcomes such as swelling, bruising, and pain.

6.3. Selection of Study Population

The following eligibility criteria are designed to select subjects for whom protocol requirements are considered appropriate. All relevant medical and non-medical conditions should be taken into consideration when deciding whether this protocol is suitable for a particular subject.

6.3.1 Inclusion Criteria

- Male or female between the age of 35 and 65 inclusive;
- Mild to Moderate Skin Laxity Severity on the submental area defined as: “normal” muscle, “mild to moderate” skin laxity and “mild to moderate” fat;
- Desire to improve jawline definitions and/or submental skin lift
- Body mass index (BMI) ≤ 30 ;
- Females of childbearing potential who are sexually active must be willing to use an approved method of birth control during study participation.
- Cooperative, reliable, and able to read and comprehend English;
- Able to read, understand, sign and date the informed consent document (English only);
- Able and willing to comply with the schedule visit(s) and study requirements.

6.3.2 Exclusion Criteria

Subjects presenting with any of the following will not be included in the study:

- Excessive subcutaneous fat on the submental area
- Use within 24 hours preceding surgery of ibuprofen, acetaminophen, any other analgesics, anti-inflammatory products, or any products including herbals and supplements that could interfere with the clinical assessments of this study (other than drugs used for anesthesia);
- History of cosmetic treatments on the face and neck including but not limited to: facial skin tightening procedures within the *past year*, injectable fillers of any type, Botox on the lower face, ablative resurfacing laser treatment, none ablative, rejuvenative laser or light treatment within the *past six months*, deep facial peels, dermabrasion, face lift, neck lift, blepharoplasty or brow lift, contour threads or other.
- History or current injury to the Head and Neck.
- Severe solar elastosis

Investigational Device: ThermiRF

Protocol No.: Thermi_0005

Version Date: Final 10-May-2016

- Clinically significant facial wounds, lesions or acute infections including cystic acne, dermatitis, lupus or other immunodeficiency affecting the dermis
- Presence of metal stents or facial implants
- Pregnant or planning pregnancy prior to the end of study participation
- Current or past history of smoking
- History or current diagnosis of cancer of any type
- History of uncontrolled cardiovascular disease(i.e. myocardial infarction, hypertension, hypercholesterolemia, peripheral vascular disease, other)
- Known hypersensitivity to local anesthetic medications
- History, or current bleeding disorders (i.e. hemophilia or von Willebrand disease), or anticipated treatment with prescription anticoagulants
- Possesses a surgically implanted electronic device (i.e. pacemaker)
- History of AIDS/HIV
- Serious mental health illness such as dementia or schizophrenia; psychiatric hospitalization in the past two years
- Developmental disability or cognitive impairment that would preclude adequate comprehension of the informed consent form and/or ability to follow study subject requirement and/or record the necessary study measurements
- A family member of the investigator or an employee of the investigator.
- Participation in any other investigational study **within 30 days prior to consent**;

In addition to the above restrictions, subject selection must be consistent with all the warnings, precautions, and contraindications associated with the ThermiRF procedures. The investigator will thoroughly familiarize him or herself with the approved labeling or manual of operations for the ID and devices used in this study.

7. TREATMENTS

7.1. Treatment Administration

The single ThermoRF treatment to the neck (right/left) will be administered by the investigator in accordance with the protocol requirements, and with adherence to Good Clinical Practices (GCP) and standard of practice for surgical procedures.

Only study subjects who signed the informed consent and meet all entry criteria, will be enrolled and treated.

7.2. Modification of Study Intervention/Investigational Product for a Subject

The output dosage is pre-determined based on the ThermoRF software algorithm. Therefore, no adjustments are planned nor anticipated.

7.3. Identity of Investigational Device and Supplies

ThermoRF is an FDA cleared device. The device is provided as a system and it includes a rectangular unit consisting of a front and rear panels, and single-use procedure kits. The system is designed to precisely deliver RF energy to target tissue. The system continuously monitors tissue temperature for patient safety using temperature controlled technology.

7.3.1 Single Use Procedure Kits

The investigator will be provided with single use procedure kits to be dispensed as one kit per study participant. The single used procedure kit consist of:

DESCRIPTION OF PROCEDURE KIT	
MODEL/ID	DESCRIPTION
S-1510-B-18	RF Disposable Cannula 15 CM length, 18 gauge, 10mm exposed tip
RFDE-15	Disposable 15 CM RF Electrode
RF-DGP-S	RF Disposable Grounding Pad

The RF Cannula and RF Electrode are sterile products and are individually packaged under sterile conditions and labeled with the commercially available label (Figure 2).

[figure not shown]
Investigational Device: ThermiRF
Protocol No.: Thermi_0005
Version Date: Final 10-May-2016

Figure 2: Primary Label Sample

For the purposes of this study, a secondary label will be applied to separate the study supplies, from the commercial product (Figure 3).

Figure 3: Secondary Label Sample

7.3.2 Other Supplies

The investigator will be permitted to use the following:

- ***Urine Pregnancy Test Kits:*** Commercially available/marketed urine pregnancy test kits and anesthesia of his/her choice.
- ***Cutometer® MPA 580:*** Commercially available standard device used to measure elasticity and other biomechanical parameters of the skin.
- ***Vectra XT System:*** a handheld 3D imaging system that delivers precision optics for high-resolution 3D images to measure contouring and area differences.

7.4. Investigational Device Storage and Accountability

The investigator must maintain adequate records documenting the receipt, use, loss, or other disposition of the ID(s). All study related supplies must be stored in a secured area or locked location and shall be accessible to the investigator or designee responsible for the conduct of this study. Used materials will be discarded by the investigator while unused materials will be returned to the sponsor at the conclusion of the study.

7.5. Blinding

This study is open-label however, photo images collected during the study will be evaluated qualitative by a panel of three qualified raters whom will be blinded (i.e., will not know) to the date and time when the photo images were collected. Each rater will evaluate the images independent of each other and will provide their respective photo image qualitative assessment for analysis.

Investigational Device: ThermiRF

Protocol No.: Thermi_0005

Version Date: Final 10-May-2016

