4.2. Secondary Objective/Endpoint

- Overall aesthetic improvement of the submental area and jawline definition at Days 90 and 180 evaluated by the investigator and subject, using the following subjective assessment:
 - Qualitative assessment based on 2D photography performed by blinded panel
 - Physician - Global Aesthetic Improvement Scale Scores (P-GAIS)
 - Subject – Global Aesthetic Improvement Scale Scores (S-GAIS)
 - Physician - Global Satisfaction Questionnaire (P-GSQ)
 - Subject - Global Satisfaction Questionnaire (S-GSQ)

Each individual endpoint will be based on study subject population response for each individual endpoint.

- Safety will be evaluated using the following measures:

- Numerical Rating Scale (NRS) a 10-point pain scale
 - Self-reported and observed adverse event

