baseline at every required time point. Additionally, every effort will be made by the investigator to ensure the same person (study staff member) will take all photos on the same subject during their participation.

- **Submental Skin Laxity Confirmation:** This assessment integrates three features: skin fat and muscle neck structures and redundancy (horizontal and vertical folds). This assessment will be performed by the investigator to ensure the subject's eligibility at Visit 1.
- **Global Assessment of Improvement Questionnaires:** A subject and physician appraisals of treatment outcomes.

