11.1. Study Hypothesis

The aim of this study is to evaluate the safety and effectiveness of the ThermiRF™ in the treatment of submental skin laxity with respect to “Lift”. The study design assumes that at least 70% of the population that consists of the target demographic (those that meet the inclusion/exclusion criteria) will have 20 mm² or more of lift. The null hypothesis is that subjects have a response rate of 45% or lower.

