11.3. Analysis Populations

- **Intent-to-Treat (ITT):** The ITT population includes all subjects that meet inclusion/exclusion criteria, have a signed informed consent form, and are enrolled in the study. The primary effectiveness analysis will be on the ITT population.
- **Safety:** The safety population will include all randomized subjects who received at least one treatment.

Investigational Device: ThermiRF

Protocol No.: Thermi_0005

Version Date: Final 10-May-2016

- **Per-Protocol Population (PPP):** The PPP will include all subjects who:

- Completed the Day 90 visit
- Have an evaluable photograph to estimate area of lift from the Day 90 visit
- Have not used an excluded medication

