11.5. Analyses

11.5.1 Primary Effectiveness Analysis

The primary effectiveness analysis will compare the proportion of subjects who respond to treatment by achieving at least 20 mm² of lift of the submental region to a null proportion 45% using a one-sided binomial proportion test at $\alpha = 0.05$. Responders will be determined based on change from baseline of area as measured by Vectra XT 3D photography in standard lighting conditions. The primary effectiveness analysis will be based on the ITT population, so any missing data, including withdrawn consent and lost to follow up, will be treated as non-response.

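### Masking to visit is specified only for the secondary 2D panel; neither document specifies it for the 3D area measurement that decides the primary endpoint

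*Protocol*

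**What the plan says.** Protocol 6.1 sets the design: "This is an open-label, single-center, single-treatment prospective evaluation of the ThermiRF device". Each subject is his or her own control (Protocol 6.2).

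The one masking provision is Protocol 7.5: "photo images collected during the study will be evaluated qualitative by a panel of three qualified raters whom will be blinded" to the date and time of the images. Protocol 4.2 lists the panel's output among the secondary endpoints: "Qualitative assessment based on 2D photography performed by blinded panel". Protocol 11.5.2 and SAP 10.2.6 also describe the panel as working on 2D photographs, and the rater validation in Protocol 11.5.2 and SAP 10.2.1 covers only 2D ratings.

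The primary endpoint is a separate, quantitative task. Lift is "defined as a ≥ 20 mm² lift of the submental area after the ThermiRF treatment" (Protocol 6.1), and Protocol 11.5.1 adds: "Responders will be determined based on change from baseline of area as measured by Vectra XT 3D photography in standard lighting conditions". SAP 4.1.1 and 10.1 carry this forward. Neither document says who derives the area, whether that person knows the visit, in what order images are measured, or which landmarks bound the region.

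Three provisions standardise image capture. Protocol 11.5.1 asks for standard lighting. Protocol 9.1 asks that baseline position and expression be replicated, and that staff "ensure the same person (study staff member) will take all photos on the same subject".

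**The concern.** As written, the endpoint that decides the trial has less stated protection against observer expectation than a secondary endpoint for which SAP 7.5 plans no formal testing in support of labelling claims.

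This matters more here than in a randomised trial. A measurement tendency that affects both arms alike partly cancels in a comparison. Here the responder proportion is compared with a fixed 45%, so a tendency to read follow-up images favourably moves subjects over the 20 mm² line and adds to the observed rate. The binomial test cannot distinguish that from a treatment effect. At stake is whether a positive primary result can be attributed to the device.

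**Working it through.** **Inputs.**
- Null rate 45%: "The null hypothesis is that subjects have a response rate of 45% or lower" (Protocol 11.1).
- 70 enrolled; one-sided exact binomial test at 0.05 (SAP 5 and 10.1).
- 70% response in subjects who stay; 12.5% dropout counted as non-response (Protocol 11.2, SAP 5).
- SD of the measured area change: not given in either document. Shifts are therefore expressed in SD units.

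**Reproducing the plan's figure.** With n = 70 and p = 0.45, P(X ≥ 38) = 0.0751 and P(X ≥ 39) = 0.0467, so success needs 39 of 70 (55.7%). The ITT alternative is 0.70 × 0.875 = 0.6125, and P(X ≥ 39 | 70, 0.6125) = 0.858. This agrees with the roughly 85% power in SAP 5.

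**Effect of a directional shift.** Take measured change as normal and let a systematic shift of b SD favour lift. A true rate p among measured subjects becomes Φ(Φ⁻¹(p) + b). The false-success probability is P(X ≥ 39) at the resulting ITT rate. Three readings of the 45% null are possible:
- A: no missing data; ITT rate = Φ(Φ⁻¹(0.45) + b).
- B: 12.5% missing, true ITT rate 45%; ITT rate = 0.875 × Φ(Φ⁻¹(0.45/0.875) + b).
- C: 12.5% missing, true rate 45% among completers; ITT rate = 0.875 × Φ(Φ⁻¹(0.45) + b).

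| Reading | b = 0: ITT rate, false success | b = 0.1 | b = 0.2 |
|---|---|---|---|
| A | 45.0%, 4.7% | 49.0%, 15.7% | 53.0%, 36.7% |
| B | 45.0%, 4.7% | 48.5%, 13.7% | 51.9%, 30.3% |
| C | 39.4%, 0.4% | 42.9%, 2.1% | 46.3%, 7.3% |

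**Without the normality assumption (no missing data).** At 45% the expected count is 0.45 × 70 = 31.5. If measurement adds 3 to that count, the rate is 34.5/70 = 49.3% and false success is about 17%. If it adds 5, the rate is 36.5/70 = 52.1% and false success is 31.7%.

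**In mm², for an assumed range of SDs (reading A).**

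| Shift | SD 10 | SD 20 | SD 40 | SD 60 | SD 100 |
|---|---|---|---|---|---|
| 2 mm² | 37% | 16% | 9% | 7% | 6% |
| 5 mm² | 95% | 50% | 20% | 13% | 9% |

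The spread shows why a shift in mm² cannot be called large or small from these documents.

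**Where an evaluability judgement can act.** Protocol 11.3 requires of the per-protocol set: "Have an evaluable photograph to estimate area of lift from the Day 90 visit". The primary analysis is ITT with missing data as non-response, so rejecting a Day 90 image normally leaves that subject a failure. The exception is the SAP rule (7.3 and 10.1) that carries a Day 60 evaluation forward when Day 90 is missing. Day 60 images exist only for the first 30 subjects (Protocol 6.1 and Appendix 1). Otherwise the judgement affects only the available-data sensitivity analysis and the per-protocol analysis.

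**The case against.** The best defence is that 3D photography is an instrument reading. Protocol 9.2 lists it as objective, and lighting, position and photographer are all controlled. These controls do limit how large a systematic shift is plausible. But they reduce noise and do not mask the measurement, and site staff who know the visit apply them. Protocol 9.2 also lists the blinded 2D panel as objective, so that label did not make masking unnecessary there. Neither document says that the area is computed automatically.

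A second defence is that Protocol 7.5 speaks of photo images without restricting them to 2D. The blinded task it describes is qualitative, however, so it does not reach an area measurement.

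A third is that counting dropouts as non-responders gives a margin. This stands in part. If 45% is the completer rate, a 0.1 SD shift gives 2.1%, below the nominal 5%. The margin disappears if 45% is the true ITT rate.

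A reader might infer more than the documents support, in three ways:
- That the 3D images are measured by someone who knows the visit. The documents are silent on this.
- That a small preference would produce a false success. Without an SD, small has no meaning in mm², and the 0.1 and 0.2 SD shifts are illustrations, not estimates.
- That evaluability judgements are generally open to influence in the primary analysis. They reach it only through the Day 60 carry-forward.

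**Conclusion.** The point holds as a missing specification with real consequences: masking is specified for the secondary 2D panel and not for the primary 3D measurement, in a design where directional bias passes undiluted into the result. If such a bias existed, the false-success probability would be 2.1% to 15.7% at 0.1 SD and 7.3% to 36.7% at 0.2 SD, depending on missing data and on whether the 45% refers to all enrolled subjects or to completers. These figures assume normally distributed change and a uniform shift. They do not show that bias is present or how large it would be. The plan should address it, but N and power are unaffected.

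**What to change.** In Protocol 7.5 and 11.5.1 and in SAP 10.1, state that:
- 3D evaluability and area are determined on coded baseline/follow-up pairs, with visit labels removed and images in random order;
- the sign of the change is assigned only after unblinding;
- where existing staffing allows, the measurer is not the person who photographed that subject, since a photographer may recognise the visit despite coding.

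The cost is some added image coding for the 3D files, which are captured separately from the 2D files, and a protocol amendment with IRB approval (Protocol 13.1). No extra subjects, procedures or readers are needed.

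Masked measurement does not remove bias introduced at image capture, so the Protocol 9.1 controls must stay, and the 4.7% error rate is not guaranteed. If the area is already measured masked, or by a fully automated routine, a sentence saying so in the same sections settles the point.

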7.6. Blinded Rater Reliability Assessment

Prior to the completion of the study, the panel of raters will undergo a validation process as defined by the sponsor using photo images collected at Day 60. The method used to evaluate and validate the reliability of the blinded panel (Appendix 10), will follow the approach taken by Kim, et al. [5], where a range of possible outcomes can be detected from “no improvement” to “some improvement” to “significant improvement” at the specified time point. The approach implemented by Kim, et. al., is deemed consistent with ICH guidelines for validation of analytical procedures.

7.7. Expected / Unexpected Risk

The anticipated risks and/or discomforts associated with the procedure are described below:

General Statement:

The device has risk of burns or fire, and therefore, cannot be used near conductive materials such as metal bed parts, inner-spring mattress, etc.

A disposable grounding pad is used to ground/neutralize the electrical current. Subjects undergoing radiofrequency treatment will be kept away from contact with metal parts which are grounded or which have appreciable capacitance to earth.

The device cannot be used in subjects with a pacemaker, implantable defibrillators, or monitoring equipment.

Risk Associate with the PRD Procedure

Known risks associated with the use of ThermiRF include:

- Erythema
- Edema
- Electric shock: operator risk only: mitigated through electrical safety testing.
- Postoperative pain and edema that resolved within three days
- Second-degree burn treatment
- Treatment induced ulcers and fistulas

Although no immediate risks are anticipated, all aspects of this clinical investigation will be conducted under the direct supervision and oversight of the investigator and designated study staff. Adverse events whether spontaneous, or self-reported, will be collected and analyzed.

Other Risk

Surgical shock, pulmonary complications, irregular surface area. Proper pre and post treatment safety precautions will reduce the risk of these complications.

Investigational Device: ThermiRF

Protocol No.: Thermi_0005

Version Date: Final 10-May-2016

Any unexpected or unforeseen complications will be managed by the investigator throughout the conduct of the study. Unforeseen or unexpected side effects not listed above will be reported to the sponsor and regulatory representatives (IRB) as they occur.

